11.42 Non-Target Lesions & Non-Target Lymph Nodes

Non-measurable sites of disease (Section 11.22) are classified as non-target lesions or non-target lymph nodes and should also be recorded at baseline. These lesions and lymph nodes should be followed in accord with 11.433.

11.43 Response Criteria

- 11.431 All target lesions and target lymph nodes followed by CT/MRI/PET-CT/ must be measured on re-evaluation at evaluation times specified in Section 11.1. Specifically, a change in objective status to either a PR or CR cannot be done without re-measuring target lesions and target lymph nodes.

Note: Non-target lesions and non-target lymph nodes should be evaluated at each assessment, especially in the case of first response or confirmation of response. In selected circumstances, certain non-target organs may be evaluated less frequently. For example, bone scans may need to be repeated only when complete response is identified in target disease or when progression in bone is suspected.

11.432 Evaluation of Target Lesions

- Complete Response (CR): All of the following must be true:
 - a. Disappearance of all target lesions.
 - b. Each target lymph node must have reduction in short axis to <1.0 cm.
 - c. Normalization of tumor biomarkers.
- Partial Response (PR): At least a 30% decrease in PBSD (sum of the longest diameter for all target lesions plus the sum of the short axis of all the target lymph nodes at current evaluation) taking as reference the BSD (see Section 11.41).
- Progression (PD): At least one of the following must be true:
 - a. At least one new malignant lesion, which also includes any lymph node that was normal at baseline (<1.0 cm short axis) and increased to ≥ 1.0 cm short axis during follow-up.
 - b. At least a 20% increase in PBSD (sum of the longest diameter for all target lesions plus the sum of the short axis of all the target lymph nodes at current evaluation) taking as reference the MSD (Section 11.41). In addition, the PBSD

- must also demonstrate an absolute increase of at least 0.5 cm from the MSD.
- c. See Section 11.32 for details in regards to the requirements for PD via FDG-PET imaging.
 - Stable Disease (SD): Neither sufficient shrinkage to qualify for PR, nor sufficient increase to qualify for PD taking as reference the MSD.
- 11.433 Evaluation of Non-Target Lesions & Non-target Lymph Nodes
- Complete Response (CR): All of the following must be true:
 - a. Disappearance of all non-target lesions.
 - b. Each non-target lymph node must have a reduction in short axis to <1.0 cm.
 - c. Normalization of tumor biomarkers
 - Non-CR/Non-PD: Persistence of one or more non-target lesions or non-target lymph nodes and/or maintenance of tumor marker level above the normal limits.
 - Progression (PD): At least one of the following must be true:
 - a. At least one new malignant lesion, which also includes any lymph node that was normal at baseline (<1.0 cm short axis) and increased to ≥1.0 cm short axis during follow-up.
 - b. Unequivocal progression of existing non-target lesions and non-target lymph nodes. (NOTE: Unequivocal progression should not normally trump target lesion and target lymph node status. It must be representative of overall disease status change.)
 - c. See Section 11.32 for details in regards to the requirements for PD via FDG-PET imaging.

11.44 Overall Objective Status

The overall objective status for an evaluation is determined by combining the patient's status on target lesions, target lymph nodes, non-target lesions, non-target lymph nodes, and new disease as defined in the following tables:

11.441 For Patients with Measurable Disease

Target Lesions & Target Lymph Nodes	Non-Target Lesions & Non-Target Lymph Nodes	New Sites of Disease	Overall Objective Status
CR	CR	No	CR
CR	Non-CR/Non-PD	No	PR

Target Lesions & Target Lymph Nodes	Non-Target Lesions & Non-Target Lymph Nodes	New Sites of Disease	Overall Objective Status
PR	CR Non-CR/Non-PD	No	PR
CR/PR	Not All Evaluated*	No	PR**
SD	CR Non-CR/Non-PD Not All Evaluated*	No	SD
Not all Evaluated	CR Non-CR/Non-PD Not All Evaluated*	No	Not Evaluated (NE)
PD	Unequivocal PD CR Non-CR/Non-PD Not All Evaluated*	Yes or No	PD
CR/PR/SD/PD/Not all Evaluated	Unequivocal PD	Yes or No	PD
CR/PR/SD/PD/Not all Evaluated	CR Non-CR/Non-PD Not All Evaluated*	Yes	PD

*See Section 11.431

** NOTE: This study uses the protocol RECIST v1.1 template dated 2/16/2011. For data collection and analysis purposes the objective status changed from SD to PR in the MCCC protocol RECIST v1.1 template as of 2/16/2011 and to match RECIST v1.1 requirements.

11.45 Symptomatic Deterioration

Patients with global deterioration of health status requiring discontinuation of treatment without objective evidence of disease progression at that time, and not either related to study treatment or other medical conditions, should be reported as PD due to “symptomatic deterioration.” Every effort should be made to document the objective progression even after discontinuation of treatment due to symptomatic deterioration. A patient is classified as having PD due to “symptomatic deterioration” if any of the following occur that are not either related to study treatment or other medical conditions:

- Weight loss >10% of body weight.
- Worsening of tumor-related symptoms.
- Decline in performance status of >1 level on ECOG scale.

12.0 DESCRIPTIVE FACTORS

- 12.1 Diagnosis: Pheochromocytoma vs. Paraganglioma
- 12.2 Baseline MIBG statuses: Positive vs. Negative vs. Unknown
- 12.3 Prior history of TKI use: Yes for this cancer or other condition vs. no vs. unknown
- 12.4 Prior chemotherapy therapy for this cancer: Yes vs. no.
- 12.5 Bone disease: Yes vs. no.
- 12.6 Secretory functional: Yes vs. no.
- 12.7 Inherited associated genetic syndrome: Yes vs. no vs. unknown
- 12.8 Bone modulating therapy (e.g., zoledronic acid, denosumab, etc.): Yes vs. no.

13.0 TREATMENT/FOLLOW-UP DECISION AT EVALUATION OF PATIENT**13.1 Continuation of treatment**

Patients who are CR, PR, or SD will continue treatment per protocol.

13.2 Progressive disease (PD)

Patients who develop PD while receiving therapy will go to the event-monitoring phase.

13.3 Off protocol treatment

Patients who go off protocol treatment for reasons other than PD will go to the event-monitoring phase per Section 4.

13.4 Complete response

If the patient has achieved CR then treatment will continue for a maximum of 5 years from time of registration.

13.5 Duration of therapy for PR or SD

Patients who are in PR or SD will continue on therapy until PD or for maximum 5 years from registration date and then they will go to event monitoring. Subsequent treatment is at the discretion of their attending physician

13.6 Progressive Disease (PD)

Patients who develop PD at any time should go to event monitoring.

13.7 Inevaluable patients

If a patient fails to complete the first cycle of treatment for reasons other than toxicity, the patient will be regarded as *inevaluable* and will be replaced.

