11.1 Schedule of Evaluations

For the purposes of this study, patients should be reevaluated every 8 weeks for the first year and then every 12 weeks after Year 1.

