16.11 Primary endpoint

The primary endpoint is the confirmed tumor response rate defined as 100% times the number of eligible patients who has started lenvatinib and whose objective tumor status was a CR or PR on 2 consecutive evaluations at least 4 weeks apart (using RECIST v1.1 criteria) divided by the number of eligible patients who has started lenvatinib.

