16.12 Operating Characteristics

The largest tumor response rate for which there would be little interest in pursuing further studies of this lenvatinib regimen in patients with progressive malignant pheochromocytoma or paraganglioma is 10%. The smallest tumor response rate for which there would be interest in pursuing further studies of this lenvatinib regimen in patients with progressive malignant pheochromocytoma or paraganglioma is 30%. The study design proposed below yields a 85% chance of detecting that the true tumor response rate is at least 30% at a 0.15 significance level when the true tumor response rate is at least 10%

16.121 Stage 1: Enter 6 eligible patients. If no tumor responses are documented among these 6 patients within the first 6 cycle of treatment, we will consider the regimen lacking in sufficient antitumor activity to recommend further testing in this patient population and terminate further enrollment. If at least one response is observed among these 6 patients within the first 6 cycles of treatment, we will proceed to Stage 2.

16.122 Stage 2: Enter an additional 17 eligible patients. If three or fewer tumor responses are documented among all 23 eligible patients within the first 6 cycle of treatment, we will consider the regimen lacking in sufficient antitumor activity to recommend further testing in this patient population. If four or more tumor responses are documented among all 23 eligible patients within the first 6 cycle of treatment, this will be considered of the regimen to have promising antitumor activity in this patient population.

We anticipate enrolling a minimum of 6 and a maximum 23 eligible. At the close of stage 1 or stage 2 enrollment, if more patients than planned have been enrolled only the first 6 eligible patients or the first 23 eligible patients enrolled, respectively, will be used to evaluate the decision rule. We anticipate accruing 2 additional patients (25 total) to account for patients found to be ineligible after signing a consent or who refused to start study treatment after signing a consent form.

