16.3 Reporting and Exclusions

- 16.31 Evaluation of adverse events.

All subjects will be evaluable for adverse events from the time of their first treatment with lenvatinib.

- 16.32 Evaluation of response.

All subjects included in the study must be assessed for response to treatment, even if there are major protocol treatment deviations or if they are ineligible. Each subject will be assigned one of the following categories: 1) complete response, 2) partial response, 3) stable disease, 4) progressive disease, 5) early death from malignant disease, 6) early death from toxicity, 7) early death because of other cause, or 9) unknown (not assessable, insufficient data). [Note: By arbitrary convention, category 9 usually designates the “unknown” status of any type of data in a clinical database.]

All of the subjects who met the eligibility criteria (with the possible exception of those who received no study medication) should be included in the main analysis of the response rate. Subjects in response categories 4-9 should be considered to have a treatment failure (disease progression). Thus, an incorrect treatment schedule or drug administration does not result in exclusion from the analysis of the response rate. Precise definitions for categories 4-9 will be protocol specific.

All conclusions should be based on all eligible subjects. Subanalyses may then be performed on the basis of a subset of subjects, excluding those for whom major protocol deviations have been identified (e.g., early death due to other reasons, early discontinuation of treatment, major protocol violations, etc.). However, these subanalyses may not serve as the basis for drawing conclusions concerning treatment efficacy, and the reasons for excluding subjects from the analysis should be clearly reported. The 95% confidence intervals should also be provided.

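### Section 13.7 replaces treated patients who leave cycle 1 for non-toxicity reasons, while Section 16 keeps them in the primary count; the two rules must be reconciled

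*Combined protocol and SAP*

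**What the plan says.** Section 13.7 reads "If a patient fails to complete the first cycle of treatment for reasons other than toxicity, the patient will be regarded as" inevaluable, and adds that the patient will be replaced. Patients who never took study drug are dealt with separately, as cancels, in 13.9b. So 13.7 concerns patients who started treatment.

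Section 16 treats the same patients differently in three places:

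- **16.11** defines the primary endpoint as confirmed responders "divided by the number of eligible patients who has started lenvatinib". It sets no condition on completing cycle 1.
- **16.12** fixes the decision set in case of over-enrolment: "only the first 6 eligible patients or the first 23 eligible patients enrolled, respectively, will be used to evaluate the decision rule". Its accrual margin is narrow: "We anticipate accruing 2 additional patients (25 total) to account for patients found to be ineligible" or who declined to start treatment.
- **16.32** lists response categories in which 4 is progressive disease, 5 to 7 are early deaths and 9 is unknown, and says: "Subjects in response categories 4-9 should be considered to have a treatment failure (disease progression"). It continues: "All conclusions should be based on all eligible subjects". Exclusions for early discontinuation are allowed in secondary analyses only, and "these subanalyses may not serve as the basis for drawing conclusions concerning treatment efficacy".

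Neither 13.7 nor Section 16 mentions the other.

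**The concern.** The trial's conclusion rests on a small count: at least 1 response in 6 patients to continue, then at least 4 in 23 to call the regimen promising. Who holds a place in the 6 and the 23 therefore matters.

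The patients covered by 13.7 are not a neutral subset. Cycle 1 lasts 28 days. Section 11.1 says "patients should be reevaluated every 8 weeks for the first year", and 16.11 requires CR or PR on two consecutive evaluations at least 4 weeks apart. Someone who leaves during cycle 1 has almost no chance of a confirmed response. Removing that patient and enrolling another exchanges a near-certain non-responder for someone who may respond. Patients who leave because of toxicity stay in and count against the drug, so the exclusion is also selective by reason.

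The plan itself foresees such patients. Section 11.45 allows progression to be declared for symptomatic deterioration without imaging, 7.6 lists withdrawal and intercurrent illness as reasons to stop, and 16.2223 has a censoring rule for a patient who starts treatment and never returns.

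**Working it through.** **Inputs.** From 16.12: null rate 10%, target 30%, stage 1 of 6 patients (stop at 0 responses), stage 2 of 17 more, promising if at least 4 of 23 respond. From 16.13: the printed table of operating characteristics. Assumed, because the documents give no figure: the share q of treated eligible patients who would be replaced under 13.7, taken as 2% to 10%. Low values are more plausible, since 3.15 requires a life expectancy above 24 weeks. Replaced patients are taken to be non-responders.

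**Step 1: reproduce the plan's figures.** With response probability p,

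P(declare) = Σ over x = 1 to 6 of P(Bin(6, p) = x) × P(Bin(17, p) ≥ 4 − x), and P(stop at stage 1) = (1 − p)^6.

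At p = 0.10:

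| x | P(Bin(6) = x) | P(Bin(17) ≥ 4 − x) | product |
|---|---|---|---|
| 1 | 0.35429 | 0.23820 | 0.08439 |
| 2 | 0.09842 | 0.51821 | 0.05100 |
| 3 | 0.01458 | 0.83323 | 0.01215 |
| 4 to 6 | 0.00127 | 1 | 0.00127 |

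The sum is 0.1488. Over p = 10, 15, 20, 25 and 30% the formula gives 0.1488, 0.3682, 0.5852, 0.7479 and 0.8523, with stage 1 stopping at 0.5314, 0.3771, 0.2621, 0.1780 and 0.1176. All agree with the printed table at two decimals. The printed design is sound for one fixed set of 6 and then 23 patients.

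**Step 2: Section 16 governs.** Every eligible treated patient keeps a place. The type I error is 0.1488, whatever q is.

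**Step 3: 13.7 governs the count.** If the overall rate among treated eligible patients is 10% and a share q of non-responders is removed, the rate among those counted is 0.10/(1 − q). Put that rate into the same formula. Expected replacements while filling 23 places are 23q/(1 − q).

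| q | rate among counted | type I error | increase over 0.1488 | expected replacements |
|---|---|---|---|---|
| 2% | 0.1020 | 0.1566 | 0.0078 | 0.47 |
| 4% | 0.1042 | 0.1649 | 0.0161 | 0.96 |
| 5% | 0.1053 | 0.1693 | 0.0205 | 1.21 |
| 10% | 0.1111 | 0.1931 | 0.0443 | 2.56 |

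The error reaches 0.155, and so stops rounding to the stated 0.15, at a counted rate of 0.10162, that is q = 1 − 0.10/0.10162 = 1.6%.

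**Step 4: direction.** The first 6 (or 23) patients left after removals include every responder among the first 6 (or 23) enrolled, because only non-responders are removed. The 13.7 count can therefore never be lower than the Section 16 count. Opposite verdicts can run one way only, and their frequency equals the increase in the table: 0.8%, 1.6%, about 2% and about 4.4% of trials at a true 10% rate. A simulation of 400,000 trials per value of q gave 0.0078, 0.0161, 0.0206 and 0.0446, with no trial in which Section 16 declared and 13.7 did not.

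**Step 5: how often the question arises.** The chance of at least one such patient among 23 is 1 − (1 − q)^23: 37% at q = 2% and 69% at q = 5%.

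**Step 6: the other reading of the rates.** If 10% and 30% were meant for patients who complete cycle 1, the 13.7 count keeps the error at 0.149. Counting all treated patients then gives a response rate of 0.30(1 − q) under the target, that is 0.294, 0.288, 0.285 and 0.270, and power of 0.842, 0.832, 0.826 and 0.796 in place of 0.852.

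**The case against.** The strongest reply is that Section 16 already settles the matter. It names the denominator, fixes the decision set at the first 6 and first 23 eligible patients even if more are enrolled, and bars efficacy conclusions from analyses that drop early discontinuations. Section 13.7 belongs to a chapter on treatment and follow-up decisions and mentions no denominator, so replacement can be read as extra enrolment only. The effect is also small at plausible rates: at q = 2%, about 63% of trials (0.98^23) would have no such patient among 23.

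Much of this stands. Section 16 does point to the all-treated count, only 16.32 uses the language of failure (under 16.11 and 16.12 these patients are non-responders in effect), and the inflation depends on staff applying 13.7 to the decision rule. The 2 extra places are an expectation, not a cap.

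It does not remove the conflict. Section 13.7 calls the patient inevaluable and does not say that the patient stays in the count, and no text says which section prevails. If replacement only means extra enrolment, it has no stated purpose, since the original patient still holds the place, and the accrual margin does not provide for it.

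**Conclusion.** The concern holds: 13.7 as written conflicts with 16.11, 16.12 and 16.32 on whether a treated patient counts towards the primary decision. The printed sample size and power are correct and are not in question. The consequence is conditional. It is nil for the type I error if Section 16 is followed. If 13.7 is applied to the count, the error is 0.157 to 0.193 over the assumed 2% to 10% range, always in the drug's favour when replaced patients are non-responders, and probably towards the lower end. That range also requires the 10% null to describe all treated eligible patients. The numerical effect is modest, but the ambiguity bears on the go/no-go decision and should be fixed before any response data are seen.

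**What to change.** State in 13.7, with a cross-reference in 16.12, that any eligible patient who took at least one dose keeps a place in the first 6 or first 23 and counts as a non-responder unless a confirmed response is documented. For the decision-rule count, limit replacement to patients found ineligible or never treated. If the sponsor still wishes to enrol 13.7 replacements, any result using them should be reported only as a subanalysis under 16.32, and the accrual allowance should be raised to include them.

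The cost is one sentence and one cross-reference, with no additional patients for the decision rule. The reported response rate may be slightly lower than under replacement. If the 30% target was intended for cycle-1 completers, the sponsor accepts the power loss in step 6 and should say which population the 10% and 30% rates describe.

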13.8 Ineligible

A patient is deemed *ineligible* if after registration, it is determined that at the time of registration, the patient did not satisfy each and every eligibility criteria for study entry. The patient may continue treatment off-protocol at the discretion of the physician as long as there are no safety concerns, and the patient was properly registered. The patient will go directly to the event-monitoring phase of the study (or off study, if applicable).

- If the patient received treatment, all data up until the point of confirmation of ineligibility must be submitted. Event monitoring will be required per Section 18.0 of the protocol.
- If the patient never received treatment, on-study material must be submitted. Event monitoring will be required per Section 18.0 of the protocol.

13.9a Major violation

A patient is deemed a *major violation*, if protocol requirements regarding treatment in cycle 1 of the initial therapy are severely violated that evaliability for primary end point is questionable. All data up until the point of confirmation of a major violation must be submitted. The patient will go directly to the event-monitoring phase of the study. The patient may continue treatment off-protocol at the discretion of the physician as long as there are no safety concerns, and the patient was properly registered. Event monitoring will be required per Section 18.0 of the protocol.

13.9b Cancel

A patient is deemed a *cancel* if he/she is removed from the study for any reason before any study treatment is given. On-study material and the End of Active Treatment/Cancel Notification Form must be submitted. No further data submission is necessary.

14.0 BODY FLUID BIOSPECIMENS

Optional blood and urine specimen for correlative studies will be collected from Mayo Clinic patients at baseline for Mayo Clinic biomarker study (IRB 13-005838) . Patient will be consented separately for the study and provided with study card for blood and urine collection. Collection, transport and processing should follow IRB 13-005838 instructions.

15.0 DRUG INFORMATION

15.1 Lenvatinib (E7080, Lenvima®)

- 15.11 **Background:** Lenvatinib is an oral, multiple receptor tyrosine kinase (RTK) inhibitor that selectively inhibits the kinase activities of vascular endothelial growth factor (VEGF) receptors VEGFR1 (FLT1), VEGFR2 (KDR), and VEGFR3 (FLT4), in addition to other proangiogenic and oncogenic pathway-related RTKs including fibroblast growth factor (FGF) receptors FGFR1, 2, 3, and 4; the platelet derived growth factor (PDGF) receptor PDGFR α ; KIT; and RET.
- 15.12 **Formulation:** Lenvatinib is available as 4 mg and 10 mg capsules. The following are capsule inactive ingredients: Calcium Carbonate, USP; Mannitol, USP; Microcrystalline Cellulose, NF; Hydroxypropyl Cellulose, NF; Hydroxypropyl Cellulose (type H), NF; and Talc, USP. The hypromellose capsule shell contains titanium dioxide, ferric oxide yellow, and ferric oxide red. The printing ink contains shellac, black iron oxide, potassium hydroxide, and propylene glycol.
- 15.13 **Preparation and storage:** Store at controlled room temperature, 25 degrees C (77 degrees F), with excursions permitted between 15 and 30 degrees C (59 and 86 degrees F)
- 15.14 **Administration:** Take lenvatinib at the same time each day with or without food. The capsules should be swallowed whole with water. Alternatively, add the lenvatinib capsules to a tablespoon of water or apple juice in a small glass to produce a suspension. Leave the capsules in the liquid for at least 10 minutes. Stir for at least 3 minutes. Drink the mixture. After drinking, add the same amount of water or apple juice (one tablespoon) to the glass. Swirl the contents of the glass a few times and swallow the additional liquid. If a patient misses a dose, and it cannot be taken within 12 hours, then that dose should be skipped and the next dose should be taken at the usual time of administration.
- 15.15 **Pharmacokinetic information:**
- Absorption:** Lenvatinib is rapidly absorbed after oral administration with t_{max} typically observed from 1 to 4 hours postdose. Food does not affect the extent of absorption, but slows the rate of absorption. When administered to healthy subjects with food, peak plasma concentrations are delayed by 2 hours.
- Distribution:** In vitro binding of lenvatinib to human plasma proteins is high and ranged from 98% to 99% (0.3 – 30 μ g/mL, mesilate). This binding was mainly to albumin with minor binding to α 1-acid glycoprotein and γ -globulin. In vitro blood to plasma ratios of lenvatinib (0.1 - 10 μ g/mL) remained constant in humans (0.589 – 0.608).
- Metabolism:** Lenvatinib is extensively metabolized in humans. The main metabolic pathways in humans were identified as oxidation by AO, demethylation via CYP3A4, glutathione conjugation with elimination of the O-aryl group (chlorbenzyl moiety), and combinations of these pathways followed by further biotransformations (eg, glucuronidation, hydrolysis of the glutathione moiety, degradation of the cysteine moiety, and intramolecular rearrangement of the cysteinylglycine and cysteine conjugates with subsequent dimerization).
- Half-life elimination:** Plasma concentrations decline bi-exponentially following C_{max} . The terminal exponential half-life of lenvatinib is about 28 hours.

Excretion: Following administration of radiolabeled lenvatinib to 6 subjects with solid tumors, approximately two-thirds and one-fourth of the radiolabel were eliminated in the feces and urine, respectively.

Special populations: No dose adjustments are required on the basis of hepatic function in patients with mild (Child-Pugh A) or moderate (Child-Pugh B) hepatic impairment. In patients with severe

(Child Pugh C) hepatic impairment, the starting dose should be lowered. No dose adjustments are required on the basis of renal function in patients with mild or moderate renal impairment. In patients with severe renal impairment, the starting dose should be lowered. Further dose adjustments may be necessary on the basis of individual tolerability.

15.16 **Potential Drug Interactions:** In vitro, cytochrome P450 3A4 was the predominant (>80%) cytochrome isoform involved in the P450-mediated metabolism of lenvatinib. In vivo, inducers and inhibitors of CYP3A4 had a minimal effect on lenvatinib exposure. Lenvatinib is not considered a strong inducer or inhibitor of cytochrome P450 or uridine 5'-diphospho-glucuronosyl transferase (UGT) enzymes. Lenvatinib may be co-administered without dose adjustment with CYP3A, P-glycoprotein (P-gp), and BCRP inhibitors or CYP3A and P-gp inducers.

15.17 **Known potential adverse events:**

Common known potential toxicities, >10%:

Gastrointestinal disorders: Abdominal pain, diarrhea, nausea, vomiting

General disorders and administrative site conditions: Asthenia

Metabolism and nutrition disorders: Decreased appetite, dehydration

Renal and urinary disorders: Acute kidney injury

Vascular disorders: Hypertension

Less common known potential toxicities, 1%-10%:

Metabolism and nutrition disorders: dehydration

Respiratory, thoracic, and mediastinal disorders: pulmonary embolism

Vascular disorders: hypotension

Rare known potential adverse events, <1% (Limited to important or life-threatening):

Blood and lymphatic disorders: Thrombocytopenia

Cardiac disorders: Acute myocardial infarction, myocardial infarction, cardiac failure, congestive cardiac failure, coronary artery occlusion, left ventricular dysfunctioion

Endocrine disorders: hypothyroidism

Gastrointestinal disorders: abdominal pain lower, abdominal pain upper, anal fistula, constipation, diverticular perforation, intestinal perforation, pancreatitis, acute pancreatitis, rectal hemorrhage, rectal perforation, stomatitis, upper gastrointestinal hemorrhage

Hepatobiliary disorders: Cholecystitis, cholecystitis acute, hepatic failure, hepatic function abnormal, hepatitis acute, hyperbilirubinemia, liver injury

Infections and infestations: Colonic abscess, perineal abscess, urinary tract infection, urosepsis

Investigations: Alanine aminotransferase increased, aspartate aminotransferase increased, blood bilirubin increased, ejection fraction increased, lipase increased, weight decreased

Metabolism and nutrition disorders: Hypocalcemia, hypokalemia, hypomagnesemia

Musculoskeletal and connective tissue disorders:

Neoplasms benign, malignant and unspecified: Intracranial tumor hemorrhage, tumor hemorrhage

Nervous system disorders: Cerebral hemorrhage, cerebral infarction, cerebrovascular accident, dizziness, hemorrhage intracranial, headache, ischemic stroke, monoparesis, reversible posterior leukoencephalopathy syndrome, subarachnoid hemorrhage, transient ischemic attack

Renal and urinary disorders: Hematuria, proteinuria, renal failure, renal impairment, renal tubular necrosis

Reproductive system and breast disorders: Female genital tract fistula, vaginal hemorrhage

Respiratory, thoracic, and mediastinal disorders: Epistaxis, hemoptysis, pulmonary hemorrhage

Vascular disorders: Hypertensive crisis

15.18 **Drug procurement**

Each participating site will order/monitor drug supply through Eisai Inc.

NOTE: Outdated or remaining drug is to be destroyed on-site per procedures in place at each institution.

15.19 **Nursing guidelines**

- 15.191 Hypertension is very common with agent. Monitor BP as per protocol and report BP elevations to the study team.
- 15.192 Diarrhea is common. This may be increased in patients who are undergoing simultaneous treatment with immunotherapy agents. Instruct patients to report any diarrhea immediately and treat symptomatically per protocol instructions.
- 15.193 Other GI side effects can occur, including decreased appetite, weight loss, and nausea/vomiting. Manage patient symptomatically and monitor for effectiveness.
- 15.194 Patients may experience fatigue. Instruct patients in energy conserving lifestyle.
- 15.195 Dermatologic related side effects have been seen, including: hand-foot syndrome, rash, and alopecia. Instruct patients to report these signs and symptoms to the study team immediately.
- 15.196 Patients may experience increased risk of bleeding. Instruct patients to report any unusual bruising or bleeding to the study team. Patients should not undergo invasive procedures without first discussing with the study team.
- 15.197 Monitor for proteinuria per protocol.

- 15.198 Rarely agent may cause decreased LVEF. Instruct patients to report any peripheral edema, DOE, chest pain or significant fatigue to the study team.
- 15.199 Monitor LFTs and renal function. Report any elevations to the provider.

